- Proximal seminal vesicles (CTVT2) shall include the proximal 2 cm of the seminal vesicles.
- In case of tumor involvement in the vesicle(s), the engaged vesicle(s) shall be outlined separately (CTVT3).
- Pelvic nodes (CTVT4) shall be delineated according to the RTOG guidelines.
- Planning Target Volume(s):
 - Prostate (PTVT1) consists of CTVT1 and a margin of 5-7 mm during the part of the treatment guided by the fiducials. During pelvic + prostate irradiation, where bone matching is used, a 10 mm isotropic margin should be applied to CTV_P.
 - **Proximal seminal vesicles (PTVT2)** consist of CTVT2 and a margin of 5-10 mm.
 - Tumor engaged vesicle(s) (PTVT3) consist(s) of CTVT3 and a margin of 5-10 mm.
 - Pelvic nodes (PTVN) consist of CTVN and an isotropic margin of 7-10 mm.
- Organs at risk (OARs)
 - The following OARs shall be delineated (structure name within parenthesis):
 - Rectum (Rectum), delineated according to the recommendations by QUANTEC¹: "The rectum should be segmented from above the anal verge to the turn into the sigmoid colon, including the rectal contents."
 - Anal canal (AnalCanal) shall be outlined as a separate volume
 - **The urinary bladder (Bladder)** shall be outlined as the outer contour of the bladder, i.e. including the muscle wall.
 - The penile bulb (PenileBulb) is defined as the oval-shaped area bounded by the crura, corpora spongiosum and the levator ani muscles (the most proximal portion of the penis) sitting approximately 1-1.5 cm caudal to the prostate. The penile bulb appears as a hyperintense oval-shaped structure on T2-weighted MR images and thus MR-based segmentation is recommended.
 - BowelBag is delineated from the level of 2 cm above the PTV-N, then drawing the whole intestinal cavity excluding muscles, vessels and internal organs (other than bowel) down to the most inferior small-or large bowel loop that is not rectum.
 - The femoral heads (FemoralHead_L and FemoralHead_R) are delineated circumferentially not including the femur neck.

PLANNING AIMS AND DOSE-VOLUME CONSTRAINTS

- Absorbed dose prescription
 - Fractionation schedules which equals to a biological equivalent of 2 Gy (BED2) to 78 Gy are allowed with dose prescriptions comparable to schedules given in Table 1. Hypofractionation schedules with fraction doses >2.5 Gy are not permitted within this protocol. Documented experience of hypofractionated schedules in published reports or quality registration is a requirement.

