 - For treatment planning optimization, the physical objectives and constraints shall be prioritized according to the examples given in **Table 2**.
- Fractionation and treatment time
 - Radiotherapy shall be given daily, 5 days per week
 - The overall treatment time shall not exceed 4 days more than an optimal treatment schedule with 7 weekdays whereof 5 treatment days per week. In case of treatment time exceeding this recommendation, corrective compensation shall be made according to local practice.

¹ Michalski JM, Gay H, Jackson A, Tucker SL, Deasy JO. Radiation dose-volume effects in radiation-induced rectal injury. Int J Radiat Oncol Biol Phys. 2010 Mar 1;76(3 Suppl):S123-9. doi: 10.1016/j.ijrobp.2009.03.078.

TREATMENT PLANNING

- The radiation treatment shall be given with 6-18 MV x-rays and with IMRT/VMAT technique.
- Treatment planning technique, e.g. delineation of help structures, and machine dependent constraints, are according to each center's treatment planning manual.

DOSE COMPUTATION

- Maximum allowed voxel size for the dose calculation grid is 3 mm in the transversal plane. A size equal to the CT slice thickness is recommended.
- The make and version of the particular treatment planning system and dose calculation algorithm shall be reported.

TREATMENT VERIFICATION

- Image-guided treatment delivery
 - The position of the fiducials in the prostate shall be estimated based on electronic kV/MV portal imaging or cone beam CT.
 - The verification and correction shall be performed prior to every treatment fraction. The treatment should start as soon as readily possible after the verification/correction.
 - The monitor units (dose) used for verification of position should be considered and compensated for if MV portal imaging is used.

ADDITIONAL CONSIDERATIONS FOR COMBINED MODALITIES

- Drug therapy
 - EBRT should begin after 12 full weeks and preferably before 14 full weeks after the date of the first LHRH agonist injection.

QUALITY ASSURANCE

- Preparatory
 - Reference dosimetry shall be carried out according to IAEA, and verified through external dosimetry audits.
 - A dummy run shall be performed before including patients in the trial. It should include delineation of structures and dose planning.
- Pre-treatment patient specific QA
 - Individual case review shall be performed according to local practice of each centre.

Fractionation	Target	Number of	Dose per	Prescribed	(EQD2 ₃) (Gy)

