schedule	structure	fractions	fraction (Gy)	total dose	
				(Gy)	
Α	PTVT1	39	2.00	78.0	(78.0)
Α	PTVT3	35	2.00	70.0	(70.0)
Α	PTVT2	25	2.00	50.0	(50.0)
Α	PTVN	25	2.00	50.0	(50.0)
В	PTVT1	29	2.50	72.5	(79.8)
В	PTVT3	29	2.30	66.7	(70.7)
В	PTVT2	29	1.80	52.2	(50.1)
В	PTVN	29	1.80	52.2	(50.1)
С	PTVT1	39	2	78	(78.0)
С	PTVT3	39	1.9	72,8	(70.0)
С	PTVT2	39	1.5	58,4	(50.0)
С	PTVN	39	1.5	58,4	(50.0)
D_SIB	ΡΤΥΤ	35	2.2	77.0	(78.0)
D_SIB	PTVN	35	1.6	56.0	(52.0)

Table 1. Dose prescriptions

In case of simultaneous integrated boost treatment (SIB) the treatment regime will be 2,2 Gy to the prostate (PTVT4) (BED2= 78 Gy, alfa/beta=3) and 1,6 Gy to elective LN (PTVN4) in 35 fractions (BED2= 52 Gy, alfa/beta=3 Gy).

CALCULATION FOR SIMULTANEOUS INTEGRATED BOOST (SIB)

Fraction dose [Gy] Nominal total dose for 35 f [Gy] EQD2 [Gy] ($\alpha/\beta = 3$ Gy) Pelvic Lymph nodes: 1,60Gy/35f Nominal dose 56Gy, EQD2 [Gy] ($\alpha/\beta = 3$ Gy) 52Gy Prostate and vesiculae seminales: 2,16Gy-2.2Gy/35f Nominal dose 76-77Gy, EQD2 [Gy] ($\alpha/\beta = 3$ Gy) 78-80Gy

 $Organs \mbox{ at risk and dose constraints for SIB 35f}$

Rectum: D5% < 72,7 GY, D20% < 68,9 GY, D50% < 59,1 GY, D60% < 49,3 GY. Not greater or less than 67,0 Gy to half of circumference and not greater or less than 49,3 Gy to entire circumference.

AnalCanal: not more than 67,0 Gy til half of circumference.

Bladder: D20% < 68,9 Gy, D50% < 64,0 Gy. Dmin (D100%) < 49,3 Gy.

FemoralHead: D50% < 49,3 Gy.

IntestinalCavity: D50% < 44,4 Gy.

BladderNeck Dmax < 72,8 Gy.

Table 2A. Dose prescription priorities for fractionation for schedule A

Priority	Structure	Prescribed	Dose-volume
		Dose (Gy)	recommendations
1	CTVT1 (Prostate)	78	D _{98%} ≥ 76 Gy (97%)
2	CTVT3 (tumor involved ves)	72.8	D _{98%} ≥ 70.7 Gy (97%)
3	PTVT1	78	D _{95%} ≥ 75 Gy (96%)
4	Rectum		V _{70Gy} < 20 %
5	PTVT1	78	D _{98%} ≥ 74 Gy (95%)
6	PTVT2	72.8	D _{98%} ≥ 68.8 Gy (94%)
7	CTVT2 (prox ves, 2cm)	58.4	D _{98%} ≥ 55.3.5Gy (95%)
8	CTVN (Nodes)	58.4	D _{98%} ≥ 55.3 Gy (95%)
9	Rectum		V _{75Gy} < 15 %
10	ΡΤVΤ3	58.4	D _{95%} ≥ 54.1 Gy (95%)
11	PTVN	58.4	D _{98%} ≥ 54.1 Gy (93%)
12	FemoralHeads_L/R		D _{2%} ≤ 51Gy
13	BowelBag		$V_{30Gv} < 300 \text{ cm}^3$
	-		$V_{40Gy} < 150 \text{ cm}^3$
			$V_{45Gv} < 100 \text{ cm}^3$
			$V_{50Gy} < 35 \text{ cm}^{3}$
14	Rectum		V _{60Gy} < 35 %
15	Body-PTV		D _{2%} ≤ 83 Gy (107%)
16	Bladder		D _{mean} ≤ 62 Gy (80%)

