Table 2B. Dose prescription priorities for fractionation for schedule B

Priority	Structure	Prescribed	Dose-volume
		Dose (Gy)	recommendations
1	CTVT1 (Prostate)	72.5	D _{min} ≥ 68 Gy (97%)
2	CTVT3 (tumor involved ves)	66.7	D _{min} ≥61 Gy (97%)
3	PTVT1	72.5	D _{95%} ≥67 Gy (96%)
4	Rectum		V _{64Gy} < 20 %
5	PTVT1	72.5	D _{98%} ≥ 66 Gy (95%)
6	PTVT2	66.7	D _{98%} ≥ 59 Gy (94%)
7	CTVT2 (prox ves, 2cm)	52.2	D _{min} ≥43Gy (95%)
8	CTVN (Nodes)	52.2	D _{min} ≥43Gy (95%)
9	Rectum		V _{69Gy} < 15 %
10	ΡΤVΤ3	52.2	D _{95%} ≥43Gy (95%)
11	PTVN	52.2	D _{98%} ≥42 Gy (93%)
12	FemoralHeads_L/R		D _{2%} ≤ 51Gy
13	BowelBag		V _{28Gy} < 300 cm ³
14	Rectum		V _{37.5Gy} < 150 cm ³
15	Body-PTV		V _{42Gy} < 100 cm ³
16	Bladder		V _{46Gy} < 35 cm ³

Priority	Structure	Dose (Gy)	Dose-volume recommendations
1	CTVT1 (Prostate)	78Gy	D _{98%} ≥ 76 Gy (97%)
2	CTVT3 (tumor involved ves)	70Gy	D _{98%} ≥ 68 Gy (97%)
3	PTVT1	78Gy	D _{95%} ≥ 75 Gy (96%)
4	Rectum		V _{70Gy} < 20 %
5	PTVT1	78Gy	D _{98%} ≥ 74 Gy (95%)
6	PTVT2	70Gy	D _{98%} ≥ 66 Gy (94%)
7	CTVT2 (prox ves, 2cm)	50Gy	D _{98%} ≥ 47.5Gy (95%)
8	CTVN (Nodes)	50Gy	D _{98%} ≥ 47.5 Gy (95%)
9	Rectum		V _{75Gy} < 15 %
10	ΡΤVΤ3	50Gy	D _{95%} ≥ 47.5 Gy (95%)
11	PTVN	50Gy	D _{98%} ≥ 46.5 Gy (93%)
12	FemoralHeads_L/R		D _{2%} ≤ 55Gy
13	BowelBag		$V_{30Gy} < 300 \text{ cm}^3$
			$V_{40Gy} < 150 \text{ cm}^3$
			$V_{45Gy} < 100 \text{ cm}^3$
			$V_{50Gv} < 35 \text{ cm}^3$
14	Rectum		V _{60Gy} < 35 %
15	Body-PTV		D _{2%} ≤ 83 Gy (107%)
16	Bladder		D _{mean} ≤ 62 Gy (80%)

Table 2C. Dose prescription priorities for fractionation for schedule C

HDR-BOOST

Patients are anesthetized and vital functions are monitored with the patient lying in dorsal lithotomy position. HDR-BT shall be performed by introducing a thread-formed iridium-192 source into hollow steel needles perforating the perineum and placed into the prostatic gland. The needles are inserted by transrectal ultrasound guidance. The treatment plan should encompass the prostatic gland (CTVT1) and 2 mm isotrope margin to the PTVT1.

Table 3

Risk organ	Brachy regime	Constraints	Fraction dose/fraction	EQD2 HDR (α/β = 3)	EQD2 HDR-External RT $(\alpha/\beta = 3)$
Urethra	10 Gy x 2	Max. 11.5 Gy to 0.1 cc	11.5 Gy / 2	66.7 Gy	116.7 Gy
Urethra	15 Gy x 1	Max 16.8 Gy to 0.1 cc	16.8 Gy / 1	66.5 Gy	116.5 Gy
Urethra	10 Gy x 2	Max point dose 12 Gy	12 Gy / 2	72 Gy	122 Gy
Urethra	15 Gy x 1	Max point dose 17.5 Gy	17.5 Gy / 1	71.8 Gy	121.8 Gy

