 - The penile bulb (PenileBulb) is defined as the oval-shaped area bounded by the crura, corpora spongiosum and the levator ani muscles (the most proximal portion of the penis) sitting approximately 1-1.5 cm caudal to the prostate. The penile bulb appears as a hyperintense oval-shaped structure on T2-weighted MR images and thus MR-based segmentation is recommended.
 - The femoral heads (FemoralHead_L and FemoralHead_R) are delineated circumferentially not including the femur neck.

Structure names in treatment planning system, Same as for primary radiotherapy treatment, se above.

RADIATION TREATMENT TECHNIQUE

The radiation treatment shall be given with external photon beam therapy with 3D-CRT and/or IMRT (VMAT) techniques. It is left to each centre to decide upon the optimal technique (number of beams, beam weights, beam angles, beam shaping, etc.).

The position shall be verified prior to every fraction with electronic kV or MV portal imaging or x-ray volumetric imaging (cone beam CT). Guidance can either be done using surgical clips or bony structures.

DOSE SPECIFICATIONS

Prescribed average dose to CTV-PB will be 66-70 Gy in 33-35 fractions over 6.5-7.0 weeks. Megavoltage equipment is required with effective photon energies ≥6MV. Minimum source-to-axis distance is 100cm.

² Michalski JM, Gay H, Jackson A, Tucker SL, Deasy JO. Radiation dose-volume effects in radiation-induced rectal injury. Int J Radiat Oncol Biol Phys. 2010 Mar 1;76(3 Suppl):S123-9. doi: 10.1016/j.ijrobp.2009.03.078.

The minimal dose to the PTV shall not be less than 95% of the prescribed dose; the maximum, not more than 105% of the prescribed dose.

Priority	Volume	Prescribed dose	
1	CTVT	D _{min} ≥ 95% D _{min} ≥ 66,5 Gy	The minimum dose to CTV-PB shall be greater than or equal to 95% of the prescribed dose, i.e. $D_{mean, PTV-P}$.
2	ΡΤντ	V _{95%} ≥ 95% V _{66,5Gy} ≥ 95%	The 95% isodose shall cover at least 95% of PTV-PB.
3	Rectum	V _{90%} ≤ 15% V63 _{Gy} ≤ 15%	Less than 15 % of the outlined rectal volume should receive doses greater than 90% of the prescribed dose.
4	ΡΤΥΤ	D _{98%} ≥ 90% D _{98%} ≥ 66 Gy	The "near minimum dose" to PTV-PB should be greater than or equal to 90% of the prescribed dose.
5	Rectum	V _{75%} ≤ 35% V52,5 _{Gy} ≤ 35%	Less than 35 % of the outlined rectal volume should receive doses greater than 75% of the prescribed dose.

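### Tables 2A–2C of the radiotherapy appendix exchange the PTVT2 and PTVT3 doses, 2A and 2C carry each other's schedule, and no target row of 2B has a Gy limit equal to its percentage.

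*Protocol*

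**What the plan says.** All places are in Protocol Appendix B.

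- **Volumes.** The section on volume selection and definition states: "Tumor engaged vesicle(s) (PTVT3) consist(s) of CTVT3 and a margin of 5-10 mm". PTVT2 is CTVT2 (the proximal 2 cm of the vesicles) plus a margin.
- **Prescription.** Fractionation is allowed "with dose prescriptions comparable to schedules given in Table 1". In schedules A, B and C, Table 1 gives PTVT3 the higher dose (70, 66.7, 72.8 Gy) and PTVT2 the lower (50, 52.2, 58.4 Gy).
- **Planning.** For optimisation, "the physical objectives and constraints shall be prioritized according to the examples given in" Table 2. Its three parts are captioned "Table 2A. Dose prescription priorities for fractionation for schedule A", "Table 2B. Dose prescription priorities for fractionation for schedule B" and "Table 2C. Dose prescription priorities for fractionation for schedule C". Each target row has a dose and a limit printed both in Gy and as a percentage.
- **Integrated boost.** "the treatment regime will be 2,2 Gy to the prostate (PTVT4) (BED2= 78 Gy, alfa/beta=3"; the calculation below it gives 78–80 Gy for 2.16–2.2 Gy per fraction.
- **Postoperative radiotherapy.** "Prescribed average dose to CTV-PB will be 66-70 Gy in 33-35 fractions over 6.5-7.0 weeks". Table 4 then prints limits in percent and in Gy.

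**The concern.** Table 2 is where a planner looks up coverage limits, and it contradicts both Table 1 and itself. As printed, the margin around an involved vesicle is held only to the elective dose. It also drops from priority 6 to priority 10, one step below a rectal limit. The proximal-vesicle PTV, in turn, must reach 66 Gy in Table 2C although the CTVT2 inside it is prescribed 50 Gy.

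The trial enrols T3 disease, so involved vesicles are relevant, and primary radiotherapy is the reference treatment. The quality-assurance section wants compliance evaluated for every patient. That is hard to do when a limit has two unequal values: a schedule B plan can pass in Gy and fail in percent.

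**Working it through.** **1. Vesicle volumes and schedules.** Prescribed doses in Gy:

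| Source | Prostate | CTVT3 | PTVT3 | CTVT2 | PTVT2 | Nodes |
|---|---|---|---|---|---|---|
| Table 1, A | 78 | – | 70 | – | 50 | 50 |
| Table 2A (captioned A) | 78 | 72.8 | **58.4** | 58.4 | **72.8** | 58.4 |
| Table 1, B | 72.5 | – | 66.7 | – | 52.2 | 52.2 |
| Table 2B (captioned B) | 72.5 | 66.7 | **52.2** | 52.2 | **66.7** | 52.2 |
| Table 1, C | 78 | – | 72.8 | – | 58.4 | 58.4 |
| Table 2C (captioned C) | 78 | 70 | **50** | 50 | **70** | 50 |

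The PTVT2/PTVT3 exchange is present in all three tables. CTVT3 minus PTVT3 is 72.8 − 58.4 = 14.4 Gy (2A), 66.7 − 52.2 = 14.5 Gy (2B) and 70 − 50 = 20 Gy (2C). The dose set of 2A is schedule C and that of 2C is schedule A; only 2B carries its own schedule. Since 2B is correctly captioned between them, a shifted caption does not explain the swap.

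**2. Gy limit against percentage.** Percentage = limit ÷ prescribed dose. Gap = printed percentage × prescribed dose − limit. The method reproduces all nine target rows of Table 2C to rounding, and eight of nine in 2A. The exception in 2A is PTVT3: 54.1/58.4 = 92.6%, printed 95%. Table 2B:

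| Row | Limit / dose (Gy) | Actual % | Printed % | Gap (Gy) |
|---|---|---|---|---|
| CTVT1 | 68/72.5 | 93.8 | 97 | 2.3 |
| CTVT3 | 61/66.7 | 91.5 | 97 | 3.7 |
| PTVT1 D95% | 67/72.5 | 92.4 | 96 | 2.6 |
| PTVT1 D98% | 66/72.5 | 91.0 | 95 | 2.9 |
| PTVT2 | 59/66.7 | 88.5 | 94 | 3.7 |
| CTVT2 | 43/52.2 | 82.4 | 95 | 6.6 |
| CTVN | 43/52.2 | 82.4 | 95 | 6.6 |
| PTVT3 | 43/52.2 | 82.4 | 95 | 6.6 |
| PTVN | 42/52.2 | 80.5 | 93 | 6.5 |

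None of nine agrees. Exchanging the PTVT2 and PTVT3 doses back gives 59/52.2 = 113% and 43/66.7 = 64%. Percentages on the EQD2 scale (29 fractions) run from 74.6 to 91.1. Neither rescues the rows. The bowel limits at the foot of 2B are not counted, because their row alignment may be an effect of reading the PDF.

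**3. EQD2 in Table 1.** EQD2 = D(D/n + 3)/5 at alpha/beta 3, as the column header states.

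- Schedule B reproduces: 79.8, 70.7, 50.1.
- Schedule C, 72.8 Gy in 39: 72.8 × (1.867 + 3)/5 = 70.9, printed 70.0.
- Schedule C, 58.4 Gy in 39: 58.4 × (1.497 + 3)/5 = 52.5, printed 50.0.
- D_SIB, 77 Gy in 35: 77 × (2.2 + 3)/5 = 80.1, printed 78.0. That value belongs to 2.16 Gy: 75.6 × (2.16 + 3)/5 = 78.0.

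The errors are 0.9, 2.5 and 2.1 Gy. On the same scale the 2A/2C swap is small: 70.9 against 70.0 for involved vesicles, 52.5 against 50.0 for nodes.

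**4. Table 4.** At 70 Gy, 95% = 66.5, 90% = 63 and 60% = 42 Gy.

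- PTVT D98% pairs 90% with 66 Gy (66/70 = 94.3%), and a bladder row pairs 90% with 65 Gy (65/70 = 92.9%).
- The second bladder row is labelled V90%, but its 42 Gy and its wording are 60%.
- The Gy values are worked for 70 Gy only. At the permitted 66 Gy, 95% is 62.7 Gy, and the printed 66.5 Gy minimum would exceed the prescription.
- The 90% limit for PTVT is looser than the 95% PTV minimum in the text above the table.

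**The case against.** The strongest reply is that the hierarchy is readable. Table 1 is titled as the prescription table, while Table 2 serves optimisation and is described as examples, with limits headed as recommendations. A PTV dosed below the CTV it contains is visibly a label slip. Read as printed, only the part of PTVT3 outside CTVT3, PTVT1 and PTVT2 would be held to the elective dose. A dummy run precedes inclusion. The quality-assurance sections list items to check without naming Table 2 as a threshold.

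Much of this stands as a limit on consequence. The 14–20 Gy figures are differences between printed prescriptions, not delivered deficits. The use of Table 2 in compliance checks is an inference. It is a fair one, because compliance, dose prescription and dose-volume histograms are to be evaluated for every patient. But Table 2 also prints doses of its own, planning is told to follow it, and no sentence says which table prevails. The dummy run is judged against a protocol that contradicts itself, and the central patient check comes after treatment is complete.

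Two points on diagnosis also deserve weight. The Gy limits of 2B divided by their percentages imply prescriptions near 70, 63 and 45 Gy (68/0.97 = 70.1; 61/0.97 = 62.9; 43/0.95 = 45.3), so one superseded dose set may explain all nine rows. The printed schedule C values arise at alpha/beta 1.5 (70.0 and 50.0). Neither makes the entries right: no schedule in Table 1 uses 70/63/45, and the EQD2 column is headed alpha/beta 3, which schedule B follows.

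Finally, the SIB calculation already gives 78–80 Gy, the wording of Table 4 is in percentages that cover 66–70 Gy, and a plan meeting the stricter 95% PTV rule meets both. Those items are minor.

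**Conclusion.** The point holds and should be fixed. All three core errors are in the printed cells: the vesicle PTVs are exchanged in three of three tables, the schedules of 2A and 2C are swapped, and nine of nine target rows in 2B contradict themselves by 3.2 to 12.6 percentage points (2.3 to 6.6 Gy). The slips in Tables 1 and 4 are real but secondary.

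The prostate dose agrees between Table 1 and Tables 2A–2C (78, 72.5 and 78 Gy). CTVT3 keeps the higher dose, and nothing shows that a patient was misdosed. Sample size, endpoint and analysis are untouched. What is at stake is consistent delivery and assessment of the reference treatment. The one assumption is that the volume definitions and Table 1 express the intent for the vesicle volumes; the CTV rows of Table 2 support it. The intended limits in 2B cannot be settled from the protocol.

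**What to change.** Amend Appendix B:

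- In Tables 2A–2C, exchange the labels PTVT2 and PTVT3, so that the involved-vesicle PTV takes the higher dose and priority 6.
- Exchange the schedule captions of 2A and 2C.
- In 2B, make Gy and percent agree; the radiotherapy leads decide which was meant. If the percentages stand, the limits in table order are 70.3, 64.7, 69.6, 68.9, 62.7, 49.6, 49.6, 49.6 and 48.5 Gy. Settle the 54.1 Gy (95%) row of 2A likewise; 95% of 58.4 Gy is 55.5 Gy.
- In Table 1, print 70.9 and 52.5 for schedule C and 80.1 for D_SIB at 2.2 Gy. If schedule C was designed at another alpha/beta, say so.
- In Table 4, correct the 66 Gy and 65 Gy entries (63 Gy at a 70 Gy prescription) and the V90% label on the 60% row. State that percentages govern for 66–70 Gy, and reconcile the 90% and 95% PTV rules.
- Add one sentence that Table 1 governs prescription.

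The cost is an appendix correction, a notice to centres and a re-check of existing RTQA evaluations against the corrected tables. No new data are needed.

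### Table 2B prints three of schedule B's four bowel-bag limits against rectum, body and bladder, leaving it no valid mid-dose rectal, hot-spot or bladder limit

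*Protocol*

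**What the plan says.** Appendix B, under planning aims and dose-volume constraints, states for plan optimisation that "the physical objectives and constraints shall be prioritized according to the examples given in" Table 2. There is one such table for each of schedules A, B and C, with 16 ranked rows. The last four rows name the same structures in all three tables.

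| Priority | Structure | Tables 2A and 2C | Table 2B |
|---|---|---|---|
| 13 | Bowel bag | V30 < 300, V40 < 150, V45 < 100, V50 < 35 cm³ | V28 < 300 cm³ |
| 14 | Rectum | V60 < 35% | V37.5 < 150 cm³ |
| 15 | Body minus PTV | D2% ≤ 83 Gy (107%) | V42 < 100 cm³ |
| 16 | Bladder | Mean ≤ 62 Gy (80%) | V46 < 35 cm³ |

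The rectum entry in Table 2B is "V _{37.5Gy} < 150 cm"³. The bladder entry in Tables 2A and 2C is "D _{mean} ≤ 62 Gy (80"%). Table 2B also has two high-dose rectal limits, V64 < 20% (priority 4) and V69 < 15% (priority 9), which correspond to V70 and V75 in the other two tables.

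**The concern.** The sequence 300, 150, 100, 35 cm³ is the bowel-bag block of the other two tables. In Table 2B it runs down four rows with four different organs. The rectum limit changes from a percentage to an absolute volume, the body limit changes from a hot-spot dose to a mid-dose volume, and the bladder limit changes from a mean dose to a small absolute volume. That pattern suggests a multi-line cell that slipped onto the rows below it and displaced their contents.

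Schedule B has the largest fraction size in Table 1 (2.5 Gy, also the protocol's ceiling) and the highest prostate EQD2 (79.8 Gy), so it is where organ limits matter most. Read literally, a planner would apply bowel limits to rectum, body and bladder and would keep only one of the four bowel limits. The quality-assurance office, which evaluates organ volumes and dose-volume histograms for every patient, could not judge a schedule B plan by the same standard as a schedule A or C plan. Adverse events and bowel and urinary quality of life are trial outcomes, so this source of variation between centres lies within one randomised arm.

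**Working it through.** **Inputs.** Table 1: schedule B gives the prostate 29 × 2.5 = 72.5 Gy; schedules A and C give it 39 × 2.0 = 78 Gy. α/β = 3 Gy, the protocol's own value. The limits are those in Tables 2A, 2B and 2C.

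**Check of the method on a stated figure.** EQD2 = D × (D/n + 3)/5. For schedule B prostate: 72.5 × (2.5 + 3)/5 = 79.75 Gy, which is the 79.8 Gy in Table 1.

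**Step 1: volumes.** Tables 2A and 2C, bowel bag: 300, 150, 100, 35 cm³. Table 2B, priorities 13–16: 300, 150, 100, 35 cm³. They are identical and in the same order. This step needs no dose model.

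**Step 2: doses as EQD2**, with n = 29 for Table 2B and n = 39 for Tables 2A and 2C.

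| Volume | Table 2B | EQD2 | Tables 2A/2C bowel bag | EQD2 |
|---|---|---|---|---|
| 300 cm³ | 28 Gy | 28 × (28/29 + 3)/5 = 22.2 | 30 Gy | 30 × (30/39 + 3)/5 = 22.6 |
| 150 cm³ | 37.5 Gy | 32.2 | 40 Gy | 32.2 |
| 100 cm³ | 42 Gy | 37.4 | 45 Gy | 37.4 |
| 35 cm³ | 46 Gy | 42.2 | 50 Gy | 42.8 |

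The largest gap is 0.6 Gy.

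**Step 3: the same conversion in reverse.** With BED = D × (1 + D/(3n)), the 29-fraction dose of equal BED is 29 × (−3 + √(9 + 12 × BED/29))/2. For 40 Gy in 39 fractions: BED = 40 × (1 + 40/117) = 53.7 Gy, giving 37.5 Gy. For 30, 45 and 50 Gy it gives 28.4, 42.0 and 46.5 Gy, against printed values of 28, 42 and 46.

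**Step 4: the intact rows.** The conversion takes rectum V70 to 64.3 Gy (printed 64) and V75 to 68.8 Gy (printed 69). It therefore reproduces the undisturbed rectal rows of Table 2B as well.

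**Step 5: a check without fraction numbers.** Scaling by 72.5/78 = 0.929 takes 30, 40, 45 and 50 Gy to 27.9, 37.2, 41.8 and 46.5 Gy. The match does not depend on the linear-quadratic model.

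**Step 6: what is missing.** Counterparts of the displaced 2A/2C entries would be about:
- Rectum V60 < 35%: V55.4 (equal BED) or V55.8 (60 × 0.929).
- Body D2% at 107%: 1.07 × 72.5 = 77.6 Gy.
- Bladder mean at 80%: 0.80 × 72.5 = 58.0 Gy (57.2 Gy by equal BED from 62 Gy).

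None of these is in Table 2B. The protocol's other organ limits are for the 35-fraction simultaneous boost, the HDR boost (Table 3) and postoperative radiotherapy (Table 4), not for schedule B.

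**Step 7: could the printed rows be intended?** Every other rectal limit in Tables 2A–2C is a percentage. A cylinder 4 cm wide (the diameter above which the appendix asks for a new planning scan to be considered) and 12 cm long (assumed) holds π × 2² × 12 = 151 cm³; at 10 to 15 cm it holds 126 to 188 cm³. A limit of 150 cm³ would thus allow most or all of even such a wide rectum to receive 37.5 Gy. A 42 Gy volume limit on the body also does not control hot spots, which is the purpose of that row in Tables 2A and 2C.

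**The case against.** **Reading fault.** The text was extracted from a PDF. If the printed bowel-bag cell has four lines, a program could have spread them over four rows and lost the true entries. This cannot be excluded without the printed page. It is unlikely, because the bowel-bag blocks of Tables 2A and 2C came through with their extra lines under blank labels, while Table 2B has exactly one value per numbered row and would have had to lose exactly three entries.

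**Number of fractions.** Table 1 gives schedule A's nodes in 25 fractions. With n = 25 the 30, 40, 45 and 50 Gy limits become 25.2, 36.8, 43.2 and 50.0 Gy EQD2, which do not match. However, the full course is 39 fractions in both A and C, and the prescribed doses printed in Table 2A (72.8 and 58.4 Gy) are those of the 39-fraction schedule C in Table 1. The volume match and the simple scaling need no fraction number.

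**Force of the table.** The protocol presents these entries as examples and recommendations, the affected rows rank lowest, the high-dose rectal and femoral-head limits are intact, and the 107% and 80% in the other tables allow a reader to guess two of the lost values. Each centre must pass a dummy run and every patient's plan is evaluated. All of this stands and lowers the consequence. It does not correct the table, and the evaluators need a correct standard to evaluate against.

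**Use.** Nothing shows that a centre used schedule B or applied these rows literally. That also stands, so harm is possible rather than shown.

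**Conclusion.** The error holds. Table 2B gives three of its 16 rows limits that belong to the bowel bag. The mid-dose rectal, hot-spot and bladder limits for schedule B are absent, and the bowel bag keeps one of its four limits. All four volumes agree exactly with Tables 2A and 2C, and all four doses agree within 0.6 Gy EQD2, assuming α/β = 3 Gy and 39 fractions for the comparison limits. The conclusion assumes that the printed page agrees with the extracted text.

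This is a transcription error in a planning table. It changes no sample size, alpha, power or primary-endpoint definition. It bears on patient safety and on uniform treatment within the radiotherapy arm, so it should be corrected, but the trial's main inference does not depend on it.

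**What to change.** 1. Check priorities 13–16 of Table 2B against the printed protocol.
2. Put all four limits (V28 < 300, V37.5 < 150, V42 < 100, V46 < 35 cm³) in the bowel-bag row.
3. Have the radiotherapy group supply schedule B limits for rectum (priority 14), body minus PTV and bladder. The values in step 6 of the working are a starting point for them to confirm, not a prescription.
4. In the same revision, compare the prescribed doses in Tables 2A and 2C with Table 1. The vesicle and nodal doses of schedules A and C appear to be exchanged between the two tables.

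The cost is one corrected table and a notice to sites that use schedule B. A short look-back by the quality-assurance group at schedule B plans already delivered is optional and can use the plan data that sites already submit.
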